4.4 Early Withdrawal of Subjects

4.4.1 When and How to Withdraw Subjects

Vaccination with the Janssen Ad26.CoV2.S vaccine will be withheld from participants from Segment I for the reasons listed below. These participants must not receive any further doses of the Janssen Ad26.CoV2.S vaccine but can remain in the study for follow-up assessments of safety and immunogenicity. Additional unscheduled visits may be performed for safety/reactogenicity reasons, if needed. In case of questions, the study staff at Mayo Arizona, Florida or Rochester are encouraged to contact the sponsor-investigator.

- Any related AE, worsening of health status or intercurrent illness that, in the opinion of the sponsor-investigator, requires discontinuation from the Janssen Ad26.CoV2.S vaccine
- The participant becomes pregnant
- Withdrawal of consent to receive the Janssen Ad26.CoV2.S vaccine
- Anaphylactic reaction following vaccination with the Janssen Ad26.CoV2.S vaccine, not attributable to causes other than vaccination
- SAE or other potentially life-threatening (Grade 4) event that is determined to be related to the Janssen Ad26.CoV2.S vaccine
- Participant previously experienced TTS or HIT
- Participant previously experienced myocarditis and/or pericarditis.

A participant will be withdrawn from the study for any of the following reasons:

- Lost to follow-up
- Withdrawal of Consent from the study
- Repeated failure to comply with protocol requirements
- Death

If a participant is withdrawn from the study, or chooses to no longer participate, no further study data will be acquired but their clinical care will continue as usual.

If a patient is withdrawn, but has already received the Janssen Ad26.CoV2.S vaccine, they will not be replaced by another patient.

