4.5 Criteria for Temporarily Delaying Administration of Study Vaccination

The following events constitute a temporary contraindication to study vaccination:

- Clinically significant acute illness at the time of vaccination. This does not include minor illnesses, such as diarrhea or mild upper respiratory tract infection.
- Fever (body temperature $\geq 38.0^{\circ}\text{C}/100.4^{\circ}\text{F}$) within 24 hours prior to the planned time of vaccination.
- An illness which in the judgement of the sponsor-investigator may interfere with reactogenicity.
- Additional adjustment needed to immunosuppression medication.

If any of these events occur at the scheduled time for receiving the first dose of the Janssen Ad26.CoV2.S vaccine, randomization at a later date within the screening window is permitted at the discretion of the sponsor-investigator.

If randomization cannot occur within the screening window, the COVID spike protein test will be repeated. If any of these events occur at the scheduled time for the second vaccination, the vaccination can be rescheduled, as long as this is in agreement with the allowed windows (see Visit Windows in the Schedules of Activities).

If the second vaccination visit cannot be rescheduled within the allowed window or the contraindications to vaccination persist, the sponsor-investigator should be contacted for further guidance.

For randomized participants who could not be administered with the Janssen Ad26.COV2.S vaccine on the day of randomization for any reason, vaccination can be administered on another day provided that vaccination occurs within the 28-day screening visit window. Baseline visit procedures should be performed prior to vaccination and within the visit window. The following study visits and procedures will be adjusted accordingly.

Participants who cannot be dosed within the 28-day screening window should be discontinued from the study and should not be rescreened.

5 Study Drug

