Participants may not have received an investigational drug within 30 days (including investigational drugs for prophylaxis of COVID-19) or used an invasive investigational medical device within 30 days or received investigational Ig or investigational monoclonal antibodies within 3 months, or received convalescent serum for COVID-19 treatment within 4 months or received an investigational vaccine (including investigational Adenoviral-vectored vaccines) within 6 months before the planned administration of the 1st dose of the Janssen Ad26.CoV2.S vaccine. During the study, the use of investigational vaccines, drugs or devices is not allowed. Treatment with investigational COVID-19 drugs after diagnosis of a COVID-19 case is allowed during the follow-up period and needs to be recorded in the COVID-19 episode description.

Licensed live attenuated vaccines should be given at least 28 days before or at least 28 days after a study vaccination. Other licensed (not live) vaccines (e.g., influenza, tetanus, hepatitis A, hepatitis B, rabies) should be given more than 14 days before (or more than 14 days after, as per Exclusion

Criteria) administration of any dose of the Janssen Ad26.CoV2.S vaccine in order to avoid potential confusion of adverse reactions and potential immune interference. If a vaccine is indicated in a postexposure setting (e.g., rabies or tetanus), it must take priority over the Janssen Ad26.CoV2.S vaccine. Receipt of any COVID-19 vaccine (outside the study) at any timepoint during the study must be recorded. The name and date(s) of administration of the COVID-19 vaccine should be recorded in the eCRF.

Subjects should not receive any pre-exposure prophylactic medications for COVID-19 until after completion of the Day 28 Visit for subjects in Segment I or the Day 84 Visit for subjects in Segment II. If pre-exposure prophylactic medication for COVID-19 is administered prior to these visits the investigator should contact the sponsor-investigator to discuss if the subject should be discontinued from the study.

The sponsor-investigator must be notified in advance (or as soon as possible thereafter) of any instances in which prohibited therapies are administered. The participant should remain in the study but receive no further study vaccination.

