7.5 Stopping Rules

Discontinuation of Study Vaccination

Study vaccinations will be withheld for the reasons listed below. These participants must not receive any further doses of Janssen Ad26.CoV2.S vaccine but should remain on study for follow-up with assessments of safety and immunogenicity as indicated in the Schedules of

Activities. Additional unscheduled visits may be performed for safety/reactogenicity reasons, if needed. In case of questions, the investigator is encouraged to contact the sponsor.

- Any related AE, worsening of health status or intercurrent illnesses that, in the opinion of the sponsor-investigator, requires discontinuation from Janssen Ad26.CoV2.S vaccine
- The participant becomes pregnant
- Anaphylactic reaction following vaccination, not attributable to causes other than vaccination
- Platelet Count <75,000 prior to receiving the Janssen Ad26.COV2.s vaccine
- SAE or other potentially life-threatening (Grade 4) event that is determined to be related to Janssen Ad26.CoV2.S vaccine
- Participant received any experimental medication (including experimental vaccines other than the Janssen Ad26.CoV2.S vaccine) or received a COVID-19 vaccine or treatment
- Withdrawal of consent to receive further study vaccination
- Participant has a molecularly confirmed SARS-CoV-2 infection based on samples collected within the study (see Section 7.2.1)
- Participant previously experienced TTS, Heparin Induced Thrombocytopenia (HIT), Myocarditis or Pericarditis.

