8.1 Confidentiality

Information about study subjects will be kept confidential and managed according to the requirements of the Health Insurance Portability and Accountability Act of 1996 (HIPAA). Those regulations require a signed subject authorization informing the subject of the following:

- What protected health information (PHI) will be collected from subjects in this study
- Who will have access to that information and why
- Who will use or disclose that information
- The rights of a research subject to revoke their authorization for use of their PHI

If a subject revokes authorization to collect or use PHI, the sponsor-investigator, by regulation, retains the ability to use all information collected prior to the revocation of subject authorization. For subjects that have revoked authorization to collect or use PHI, attempts should be made to obtain permission to collect at least vital status (long term survival status that the subject is alive) at the end of their scheduled study period.

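### Section 4.5 removes from the study randomized patients who miss the dosing window, even after the study has cut their immunosuppression, in conflict with 7.5 and with the safety endpoints counted from randomization

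*Combined protocol and SAP*

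**What the plan says.** Section 4.5 lets a randomized patient who cannot be vaccinated on the planned day be vaccinated later within a 28-day screening window. It then says: "Participants who cannot be dosed within the 28-day screening window should be discontinued from the study and should not be rescreened". One of its four reasons for delay is "Additional adjustment needed to immunosuppression medication". For a second dose that misses its window, the same section says only that "the sponsor-investigator should be contacted for further guidance".

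In the adjustment arm the reduction comes before the dose. Section 6.1.2 starts it on Day -14 (+/-3 days), and 6.1.3 puts the dosing visit at Day 0 (-4/+1 day). Section 5.2.1 times the return to prior doses at 28 days after vaccination.

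Other sections treat withheld vaccination differently:
- 7.5: such patients "should remain on study for follow-up with assessments of safety and immunogenicity".
- 4.4.1: they "can remain in the study for follow-up assessments of safety and immunogenicity".
- 5.6, after a prohibited therapy: "The participant should remain in the study but receive no further study vaccination".
- 8.1, for patients who revoke authorization: "attempts should be made to obtain permission to collect at least vital status".

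For patients who are withdrawn or leave, 4.4.1 says that "no further study data will be acquired but their clinical care will continue as usual", and 4.4.2 agrees.

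**The concern.** The reduction of immunosuppression is the randomized intervention, and it starts before the vaccine is given. A patient can have mycophenolate or azathioprine stopped because of the study, miss the dose, and then leave study follow-up. Section 1.5.9 says that the actual risk of the reduction is unknown, so these patients belong in its safety record.

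Section 3.6 counts hospitalization, patient survival and graft survival to 2 years from randomization. It also lists rejection, graft loss and new donor-specific antibody as harms of the reduction. Section 1.5.9 pauses the study at a 10% rejection rate. Events that arise after discontinuation would be missing from all of these. The loss could also differ by arm, because a need for further immunosuppression changes may arise more often in the adjustment arm; that is an inference.

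**Working it through.** **1. Does the rule reach randomized patients?** Yes. The sentence just before it concerns randomized patients not vaccinated on the planned day, and no exception follows.

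**2. Is there a conflict within the plan?** The 7.5 list includes a platelet count below 75,000 before the vaccine, and also pregnancy and intercurrent illness. Each can block a first dose. A patient with persistently low platelets at Day 0 is to stay on study under 7.5 and to be discontinued under 4.5. Sections 4.4.1 and 5.6 are weaker support: the first is permissive, and the second concerns prohibited therapies. A missed dosing window is not among the reasons for study withdrawal in 4.4.1.

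**3. Do other sections recover the data?**
- 7.3: general SAE reporting starts at first vaccination, so it never starts for an undosed patient. Procedure-related events are reported from consent, but only until early withdrawal.
- 7.1: rejection, donor-specific antibody and graft loss are followed for the study duration only in vaccine recipients.
- 6.9: secondary analyses use the all-treated population.
- 1.5, 7.1 and 7.3: events already present at discontinuation are still followed. The gap is new events.

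**4. Exposure by the planned dosing visit** (6.1.2, 6.1.3, 5.2.1; the two windows are assumed to vary independently).
- Adjustment starts between -14 - 3 = Day -17 and -14 + 3 = Day -11. The dosing visit falls between Day -4 and Day +1.
- Shortest: -4 - (-11) = 7 days. Nominal: 0 - (-14) = 14 days. Longest: 1 - (-17) = 18 days.
- The planned course is 14 + 28 = 42 days, so these are 7/42 = 17%, 14/42 = 33% and 18/42 = 43% of it.

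**5. Size.** The plan gives no rate of undosed patients. Assume 2% to 5% of the 150 in the adjustment arm.
- Patients: 0.02 × 150 = 3; 0.05 × 150 = 7.5.
- Rejections, at the 10% that 1.5.9 gives as an upper bound: 3 × 0.10 = 0.3; 7.5 × 0.10 = 0.75.
- For scale, a 10% rate in 150 patients is 0.10 × 150 = 15.

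**6. Primary comparison.** Section 6.7 states 90% power for 20% versus 37% with 150 per arm, two-sided 0.05, arcsine effect size. With h = 2·asin(√0.37) − 2·asin(√0.20) and power = Φ(h/√(1/n1 + 1/n2) − 1.96), I obtain 0.909, so the figure reproduces. With 142 patients in the adjustment arm (5% undosed and dropped) it is 0.901. Under 6.9 undosed patients are outside the all-completed population whether or not they are followed, so the change proposed here does not alter that analysis.

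**The case against.** The strongest reply has four parts.

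- **The bar on further doses in 4.4.1 and 7.5 suits patients already dosed.** This is fair for much of the wording, but the low-platelet item in 7.5 is explicitly before the dose, so the conflict stands. A missed second dose and revoked authorization are different situations and serve only as context.
- **Equating discontinued with withdrawn is not stated.** Correct. It is the likely reading, and the loss of data depends on it. If sites read 4.5 otherwise, or apply 7.5 first, the gap shrinks to delays that outlast the window and meet no listed reason.
- **Section 4.5 is not the only cause.** Correct. Sections 7.1 and 6.9 also restrict attention to vaccinated patients, so changing 4.5 alone would not repair the endpoints.
- **The size is negligible and probably overstated.** Largely fair. The 10% comes from reductions usually longer than 6 weeks, the illustration counts rejections that would be followed anyway, and the 7 to 18 days describe the planned visit, not the moment of discontinuation.

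Three stronger readings are tempting, and the documents do not support them:

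- **Many patients would be caught.** Screening may be as early as Day -21 - 30 = Day -51, so a Day 0 dose could already fall 51 - 28 = 23 days past a 28-day window. But the plan does not say when that window starts.
- **Patients are abandoned on reduced immunosuppression.** Clinical care continues under 4.4.1, a nephrologist sets each adjustment under 5.2.1, and 1.5.9 describes a transient 6-week change. What is missing is one sentence for a cancelled dose.
- **The rule biases the primary result.** The exclusion of undosed patients there comes from the completer definition in 6.9, which is a separate choice.

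**Conclusion.** The concern holds as a minor point. Section 4.5 orders the discontinuation of undosed randomized patients with no exception for those already on reduced immunosuppression. That conflicts with 7.5 and fits poorly with the endpoints that 3.6 counts from randomization. Sections 7.1 and 6.9 widen the gap.

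The consequence is incomplete capture of new harms after discontinuation, provided that discontinuation is handled as withdrawal. The number of patients is unknown and probably small; the 3 to 7.5 patients and 0.3 to 0.75 rejections rest on an assumed 2% to 5% undosed and an upper-bound risk. The primary safety endpoint, SAEs related to the vaccine, cannot be affected by patients who never received it. Confidence is moderate.

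**What to change.** - **4.5:** for randomized patients in both arms, replace discontinuation with an instruction that the patient is not vaccinated but stays on study for safety follow-up unless consent is withdrawn. Collect patient and graft status, hospitalization and rejection by contact or through the Year 1 and 2 record review in 6.1.7, anchored to randomization.
- **7.1 and 7.3:** follow and report rejection, de novo donor-specific antibody and graft loss from the start of adjustment in all randomized patients, not only vaccine recipients.
- **6.9:** analyse the 3.6 endpoints that are counted from randomization, and the harms of the reduction, in the all-randomized population that the section already defines.
- **5.2.1, as a secondary clarification:** state that prior immunosuppression resumes if the dose is cancelled, on a schedule that the sponsor sets.

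The cost is a few sentences in four sections, record-review follow-up of a few undosed patients, and a new anchor date for them, because the Day 28, 90 and 180 visits count from vaccination.

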5.1 Description

The Janssen Ad26.CoV2.S vaccine is a monovalent vaccine composed of a recombinant, replication-incompetent human adenovirus type 26 (Ad26) vector that encodes a SARS-CoV-2 spike (S) protein in a stabilized conformation. The S protein on the surface of the coronavirus binds to the Angiotensin Converting Enzyme 2 (ACE2) receptor of a host cell allowing the virus to infect the cell. Vaccination with the Janssen COVID-19 Vaccine leads to humoral and cellular immune responses directed against the S protein and in particular the production of neutralizing and other functional S antibodies which may block ACE2 receptor binding to the S protein, contributing to protection against COVID-19.

COVID-19 and SARS-CoV-2

COVID-19 is an infectious disease of the respiratory tract caused by SARS-CoV-2. SARS-CoV-2 carries RNA as its genome. The genome consists of 6 major open reading frames and accessory genes coding for non-structural proteins, including the RNA-dependent RNA polymerase, proteases, and the structural proteins, including the matrix (M), envelope (E), spike (S), and nucleoprotein (N). The spike (S) protein is responsible for binding to the human cell surface receptor, followed by membrane fusion and entry.

Viral Vector-based Vaccines

Viral vector-based vaccines do not contain antigens, but rather use the body's own cells to produce them. Adenoviruses are among the most utilized vectors for vaccine development. The viral vector is replication incompetent so the viral DNA cannot replicate and will over time be cleared from the cells/tissues, e.g. due to cell division, or due to removal of transduced cells by the immune system. Nonclinical biodistribution studies show that adenoviral vector DNA of Ad26 vaccine vectors did not distribute widely, as the vector DNA was primarily detected at the site of administration in the muscle, the draining lymph nodes and, to a lesser extent, to the spleen. Viral vector DNA can be detected in tissues at very low levels for weeks until a few months after vaccination in animal models. Antigen expression data for the S protein are not available, but in animals the expression of another antigen delivered with the Ad26 vector cannot be detected after 1-2 weeks.

Janssen selected the human adenovirus-26 (Ad26) as a vector for the SARS-CoV-2 antigen because of the substantial nonclinical and clinical evidence from Janssen's other vaccine development programs. Across Janssen programs, Ad26-based vaccines demonstrate the capacity to elicit strong humoral immune responses with both neutralizing activity and non-neutralizing antibody functionalities, and cellular immune responses involving both CD8+ T cells and CD4+ T cells, with predominantly a Th1 phenotype.

The Janssen COVID-19 Vaccine includes the following ingredients: recombinant, replication-incompetent adenovirus type 26 expressing the SARS-CoV-2 spike protein, Sodium chloride, Citric acid monohydrate, Polysorbate 80, 2-hydroxypropyl-β-cyclodextrin (HBCD), Ethanol (absolute), Sodium hydroxide and Water for injection (WFI).

5.2 Treatment Regimen

5.2.1 Immunosuppression Adjustment

Immunosuppression adjustment will occur 2 weeks prior to receiving the Janssen Ad26.COV2.S vaccine and continue for 28 days receiving the Janssen Ad26.COV2.S vaccine.

Given that transplant patients are maintained on immunosuppressive regimens that vary slightly, immunosuppression adjustment will need to be somewhat individualized to the patient. However, general rules can be implemented.

Two weeks prior to receiving the Janssen Ad26.COV2.S vaccine, patients randomized to immunosuppression adjustment (or offered immunosuppression adjustment in Segment II) will be considered individually and adjustments will be made by a nephrologist with knowledge of the patient's clinical situation. General rules for adjustment are as follows:

1. For patients receiving mycophenolate mofetil (MMF) or azathioprine (AZA), a calcineurin inhibitor (CNI) (typically tacrolimus or cyclosporine), and Prednisone. Adjustment will involve stopping MMF or AZA and starting 10 mg Prednisone/day. **Note:** most patients will be in this group.
2. For patients not on MMF, but on CNI and Prednisone, the CNI dose will be decreased by 50%,
3. For patients on belatacept, which is typically taken with MMF and Prednisone, MMF will be stopped, and belatacept and Prednisone will be modified to 10 mg a day.
4. Other patients are adjusted on a case-by-case basis by the sponsor-investigator and the co-investigators—ex. Tac-mTOR inhibitor—Reduce Tac by 50%.

28 days after receiving the Janssen Ad26.COV2.S vaccine, study subjects in this arm will resume their prior doses of immunosuppression and will be followed as per protocol and as clinically indicated by the transplant team.

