6.1 Segment I

6.1.1 Day - 21 (-30 /+7 Days)

Potential subjects will be identified by review of their medical record. If a participant is identified by review of the report, they will be contacted via the Mayo Clinic portal, the online patient communication system, phone or e-mail (if the potential subject has already contacted the study team in this manner). Study details, procedures, risks, and benefits will be described to patients interested in participation. Subjects will be consented for study participation either via telephone or at Mayo Clinic, depending on patient preference. The participant's medical history, demographics, concomitant medications and therapies, immunosuppression medications and clinical outcomes (current health and graft status) will be collected. Subjects will complete the COVID-19 Surveillance and Evaluation questionnaire (Section 14.6). Relevant medical procedures which are performed as part of the participants clinical care up to 60 days prior to signing of consent, such as clinical laboratory results may be used for determining study eligibility.

Blood for anti-SARS-CoV-2 spike protein antibody and anti-SARS-CoV-2 nucleocapsid total antibody testing will be drawn locally and sent overnight to Mayo Clinic-Rochester Laboratory for

testing. Not all screening procedures need to occur in one day. After consent is obtained, screening procedures can be completed on any day up to the baseline visit.

Patients who meet criteria will be contacted and scheduled to receive the Janssen Ad26.CoV2.S vaccine. They will be required to travel to one of the 3 Mayo Clinic transplant centers to receive the vaccine. There will be 3 groups:

1. Low-responders (n=100)
2. Non-responders (n=300)—Randomized after obtaining evidence that anti-SARS-CoV-2 spike protein antibody levels = 0 U/mL. Patients are stratified by the number of mRNA vaccines they received (2 or more).
 - a. Dosing with the Janssen Ad26.COVID-19 vaccine without immunosuppression adjustment
 - b. Dosing with the Janssen Ad26.COVID-19 vaccine with immunosuppression adjustment.

Subjects randomized to receive immunosuppression adjustment will follow one of the regimens outlined in Section 5.2.1. If randomized to the immunosuppression group, they will be contacted via phone by a physician with instruction on the participant's new immunosuppression regimen.

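### The Section 5.2.1 adjustment rules need rewording: rule 1 requires the Prednisone it then starts, and rule 3 gives belatacept and Prednisone one shared daily dose

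*Combined protocol and SAP*

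**What the plan says.** Section 5.2.1 of the combined protocol and SAP gives four rules, which it calls general.

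- **Rule 1** applies to patients on MMF or AZA, plus a CNI, plus Prednisone. The action is "Adjustment will involve stopping MMF or AZA and starting 10 mg Prednisone/day". No CNI change is stated. A note adds that "most patients will be in this group".
- **Rule 2** reads "For patients not on MMF, but on CNI and Prednisone, the CNI dose will be decreased by 50" percent. AZA is not mentioned.
- **Rule 3** applies to patients on belatacept, described as typically taken with MMF and Prednisone: "MMF will be stopped, and belatacept and Prednisone will be modified to 10 mg a day".
- **Rule 4** is the fallback: "Other patients are adjusted on a case-by-case basis by the sponsor-investigator and the co-investigators". Its example is tacrolimus with an mTOR inhibitor, where tacrolimus is halved.

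The same section says that patients "will be considered individually and adjustments will be made by a nephrologist" who knows the clinical situation, and that prior doses resume 28 days after vaccination. Section 6.1.1 adds that "Subjects randomized to receive immunosuppression adjustment will follow one of the regimens outlined in Section 5.2.1" and that "they will be contacted via phone by a physician" with the new regimen.

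Section 1.5.9 describes standard maintenance at the three sites as two or three drugs: a CNI with mycophenolate, and Prednisone only in some patients. It gives the addition of Prednisone on stopping mycophenolate as an example of a change, and it promises that every patient stays on at least two drugs.

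**The concern.** These rules define the randomized intervention in Segment I and the adjustment in Segment II. At three sites, they are the text a physician consults before changing a transplant recipient's drugs.

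Rule 1 is said to hold most patients, yet its entry condition and its action do not fit together. A patient who meets the condition already takes Prednisone, so there is nothing to start. The patient for whom starting it makes sense does not meet the condition. For those already on Prednisone, rule 1 does not say whether 10 mg/day replaces the existing dose. Rule 3 uses a different verb for the same drug, and its one dose phrase grammatically covers belatacept as well.

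What is at stake is a consistent intervention and clear dosing. Section 1.5.9 accepts that transient adjustment may raise the risk of rejection or graft loss, so the dosing text should not need interpretation.

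**Working it through.** No figure in the plan depends on these rules, so the check sets regimens against the literal conditions.

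**Inputs.** The conditions and actions of rules 1 to 4 come from Section 5.2.1. The two-drug floor and the description of standard care come from Section 1.5.9.

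**Step 1: which rule does each regimen meet?** MMF and AZA are taken as not given together. The first five rows are without belatacept.

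| Regimen before adjustment | Rule met, read literally | Consequence |
|---|---|---|
| MMF + CNI + Prednisone | 1 | Stop MMF; start Prednisone that is already being taken |
| MMF + CNI | 4 | Rule 1 fails (no Prednisone), rule 2 fails (on MMF), rule 3 fails (no belatacept) |
| AZA + CNI | 4 | Rules 1 and 2 both need Prednisone |
| AZA + CNI + Prednisone | 1 and 2 | Rule 1: stop AZA, no CNI change stated. Rule 2: CNI at 50%, AZA not mentioned |
| CNI + Prednisone | 2 | Halve the CNI |
| Belatacept + MMF + Prednisone | 3 | Stop MMF; one 10 mg daily dose for two drugs |

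Every patient who meets rule 1 is already on Prednisone. The MMF + CNI patient, part of standard care in Section 1.5.9 and the case behind its example, is outside rules 1 to 3.

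**Step 2: what does the two-drug floor imply about intent?**

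- MMF + CNI: stopping MMF leaves 2 − 1 = 1 drug. Adding Prednisone gives 1 + 1 = 2. The floor is met only if a drug is added, which agrees with the Section 1.5.9 example.
- Belatacept + MMF + Prednisone: 3 − 1 = 2 drugs. Belatacept must be kept to meet the floor, so the intent can be inferred, but no section states its dose.
- Belatacept + MMF without Prednisone (possible, since rule 3 says only typically): 2 − 1 = 1 drug unless Prednisone is started. A revised rule 3 therefore needs a start instruction as well as a modify instruction.

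**Step 3: does any design figure move?** Section 6.7 states power 0.9 for 20% versus 37% with 150 per arm. With the arcsine effect size h = 2·|asin√0.20 − asin√0.37| = 0.3805, power = Φ(h·√(150/2) − 1.960) = Φ(3.295 − 1.960) = 0.909, in agreement. The inputs are response rates, arm size and alpha. The wording of Section 5.2.1 does not enter.

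**The case against.** The strongest reply is that these are general rules, not an algorithm. Section 5.2.1 says adjustment is individualized and made by a nephrologist. Section 6.1.1's reference to the regimens of Section 5.2.1 includes rule 4, so every patient has a route. Starting 10 mg/day can be read as starting that dose, which is compatible with already taking another. The resumption of prior doses after 28 days fits a temporary dose change. The Day −14 contact (Section 6.1.2) documents and instructs the regimen, and Schedule of Events 2C records immunosuppression again at Days 0, 14 and 28, so variation would be visible.

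Most of this stands and is why the point is minor. It does not settle whether 10 mg replaces or adds to an existing Prednisone dose, or what happens to belatacept. The nephrology consults before vaccination (Sections 6.1.3 and 6.2) confirm compliance with the regimen given, not which rule should have supplied it.

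A reader might infer three stronger things that the documents do not support.

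- *That AZA + CNI + Prednisone patients truly have two open regimens.* Rule 1 comes first, names AZA and says to stop it. Rule 2 gives no AZA instruction. The overlap is a drafting gap, and rule 1 is the evident intent.
- *That belatacept would be given at 10 mg a day.* Nephrologist control and the two-drug floor point to continuing it. No realistic path to that dosing is shown.
- *That 150 to 400 adjustments are affected.* Those figures are the 150 patients in the adjusted arm plus 0 to 250 in Segment II (Section 3.1.2), that is, 150 + 0 = 150 to 150 + 250 = 400. They count everyone the section governs, not anyone misdirected. With the protocol's illustrative 100 in Segment II, the governed number is 150 + 100 = 250.

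**Conclusion.** Section 5.2.1 is wrong as written, and the fault is minor. Rule 1 contradicts its own entry condition and does not fit Section 1.5.9. Rule 3 assigns one dose to two drugs and leaves belatacept without an instruction. The AZA overlap between rules 1 and 2 is secondary.

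The size cannot be put as a patient count, because the documents give no mix of maintenance regimens. Individualization by a nephrologist and rule 4 limit the practical harm. The randomized comparison, its power and the sample size are unchanged.

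The conclusion about rules 1 to 3 rests only on their literal text. The reading of intent assumes that the Section 1.5.9 example and two-drug floor apply to every adjusted patient.

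**What to change.** Reword the three rules as follows.

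- **Rule 1:** Patients on MMF or AZA plus a CNI, with or without Prednisone: stop MMF or AZA. If not on Prednisone, start 10 mg/day; otherwise modify Prednisone to 10 mg/day.
- **Rule 2:** Patients on a CNI and Prednisone who take neither MMF nor AZA: halve the CNI dose.
- **Rule 3:** Patients on belatacept: stop MMF and continue belatacept at a stated dose. If not on Prednisone, start 10 mg/day; otherwise modify Prednisone to 10 mg/day.

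Rule 4 stays as it is. With this text, AZA + CNI + Prednisone meets rule 1 only, and MMF + CNI moves from rule 4 to rule 1 and ends on two drugs. Belatacept + MMF ends on two drugs whether or not the patient was taking Prednisone.

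Two points are clinical, and the sponsor's transplant physicians must confirm them before the text is final: that 10 mg/day replaces an existing Prednisone dose, and the belatacept dose. The cost is those two confirmations and three reworded rules in one amendment. No extra patients, visits, CRF fields or tables are needed.
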